6.5. Extent of Exposure

Extent of exposure to GSK2857916 will be summarized.

The number of cycles administered to study treatment will be summarised with mean, median, standard deviation, minimum, and maximum. The number and percentage of subjects who received a given number of cycles (<4, 4, and >4 cycles) will be reported.

Dose intensity (dose delivered per cycle) will be summarized using mean, median, standard deviation, minimum, and maximum by cycle and overall. Dose intensity is the cumulative actual dose divided by the total number of cycles across the entire treatment period. A by subject summary listing of data on exposure to all study treatments will be produced.

Dose reductions will be summarised by number of reductions and reasons for reductions. Dose delays will be summarised by number of delays, reasons for the delays, and delay duration (days). The number and percentage of the delays 1-21, 22-42 and >42 days will be computed. Primary reasons for dose reductions and dose delays will also be summarized by cycle.

Duration of delays is defined as period from the expected start date of dose to actual start date of current dose. Calculation: (actual start date of current dose - expected start date of dose). Expected start date of dose = actual start date of previous dose + 21.

The summaries of dose modifications will be provided only if the data warrant.

All the dose reductions, dose escalations, infusion interruptions, incomplete infusions and dose delays will be listed separately.

A plot showing the number and percentage of subjects treated at different dose levels over time will be provided.

The duration of exposure to study treatment in days (from first day to last day of treatment) will be calculated. A horizontal bar graph of duration of treatment will be produced that displays duration of treatment in days for each subject.

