
 Refer to Section 9.3.2.
Model Results Presentation

 Power Model 
 The mean slope and the corresponding 90% confidence interval for each parameter will be produced in tabular format. Comparative plots of individual PK parameters will be generated by treatment on linear and semi-logarithmic scales. Supportive SAS output from statistical analysis will be generated.

9.3.1.2. Assessment of Accumulation Ratio:

To assess the extent of accumulation following GSK2857916 repeat dosing, the observed accumulation ratio (Ro) for GSK2857916, total antibody, unbound antibody, and cys-mcMMAF will be determined as ratio of C_{max} and C_{trough} at steady-state to C_{max} and C_{trough} after the first dose, respectively, adjusted for any change in GSK2857916 dose.

$$Ro (C_{max}) = C_{max} C_{xD1} / C_{max} C_{1D1};$$

x = 3, 5;

$$Ro (C_{trough}) = C_{trough} C_{xD1} / C_{trough} C_{1D1};$$

x = 3, 5;

Preliminary pharmacokinetic data indicate that the pharmacokinetics for the third consecutive dose given at the planned interval will be at steady state. Therefore, based

on the study design, subjects who meet one of the following criteria will be at steady state:

- Subjects who receive the same dose without delay or change for Cycles 1, 2, and 3 (i.e., with dosing delays of ≤ 3 days). In this case, Cycle 3 represents steady state. Accumulation ratios are calculated as Cycle 3/Cycle 1.
- Subjects who receive the same dose without delay or change to Cycle 5. Accumulation ratio = Cycle 5/Cycle 1.
- Subjects who have a dose reduction or two by Cycle 3, but then dose is maintained at the same level and interval through Cycle 5. Cycle 5 represents steady-state pharmacokinetics, but dose adjustment is needed. Dose adjustment: multiply C_{max}/C_{trough} values by the ratio (starting dose level/Cycle 3-5 dose level). Accumulation ratio = adjusted Cycle 5/Cycle 1.

For the purpose of accumulation ratio analysis, C_{max} is defined as the EOI concentration at each cycle.

Exploratory analysis might be performed considering the effect of dose delay on the ratio.

Accumulation Ratio Assessment (Part 1 and Part 2)
Endpoint(s)

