
 • Accumulation ratio (R_o). The observed accumulation ratio (R_o) will be calculated for each analyte by determining the ratio of C_{max} at steady state to C_{max} on Day 1 ($R_o(C_{max})$) and the ratio of C_{trough} at steady state to C_{trough} on Day 1 ($R_o(C_{trough})$).
Model Specification

 • A mixed effect model will be fitted for each parameter by actual dose at each cycle as fixed effect and subject as random effect. The model will be adjusted by actual dose and dose delay status in each cycle. The ratio will be calculated by back-transforming the difference between the Least Squares means. Using the pooled estimate of variance, 90% confidence intervals will be calculated for the difference and then back-transformed. • The Kenward & Roger degrees of freedom approach will be used.
Model Checking & Diagnostics

 • Refer to Section 9.3.2.
Model Results Presentation

 • Geometric least-squares means for each treatment, point estimates and associated 90% confidence intervals for the ratios for each parameter will be produced in tabular format. • Plots of mean Accumulation Ratio will be generated by dose group on linear and semi-logarithmic scales. • The accumulation ratio will be listed and summarized along with other PK parameters. • Supportive SAS output from statistical analysis will be generated.

9.3.1.3. Assessment of Analyte Ratios:

Following natural log-transformation, C_{max} and C_{tau} of ADC, unbound and total antibody, and cys-mcMMAF will be analysed using a mixed effects model with fixed effect terms for treatment, visit, and $\log(\text{body weight})$. Subject will be treated as a

random effect in the model. Point estimates and their associated 90% confidence intervals will be constructed for the differences of Cmax and Ctau in analytes and comparison with cys-mcMMAF at each cycle. The point estimates and their associated 90% confidence intervals then will be back-transformed to provide point estimates and 90% confidence intervals for the ratios of analytes to cys-mcMMAF at each cycle.

Ratio of analytes at each cycle versus cys-mcMMAF at Cycle X:

$$Ra (Cmax) = \frac{Cmax (ADC, unbound anti-body, total anti-body) Cycle X}{Cmax (cys-mcMMAF) Cycle X}$$

X = 1, 2, 3, 5;

$$Ra (Ctrough) = \frac{Ctrough (ADC, unbound anti-body, total anti-body) Cycle X}{Ctrough (cys-mcMMAF) Cycle X}$$

X = 1, 2, 3, 5;

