16. Sample(s) collected for analysis at central lab. The same sample will be used for BCMA (flow) and PD. On D8 only postdose PD assessment will be performed, if applicable (refer to footnote 18).
17. FISH testing at least for: t(4;14), t(14;16), 17p13del. FISH results from samples taken within 60 days prior to first dose are acceptable.
18. **Additional samples may be collected in some subjects (up to 6) for further exploration of PD.**
19. Archival tissue from up to 60 days prior to study is acceptable.
20. Collect sBCMA at C1D1 predose (within 30 minutes prior to SOI) and at EOI (± 5 minutes), C2D1 at predose (within 30 minutes prior to SOI) and at EOI (± 5 minutes).
21. Collect cytokines at predose (within 30 minutes prior to SOI) and EOI (± 5 min) (even when infusion is interrupted or halted) to assess allergic reaction
22. All ADA samples will be collected prior to each infusion
23. Flow cytometry performed central laboratory.
24. PK samples to be taken for both GSK2587916 and cys-mcMMAF measurement on C1D1, C2D1, C3D1, and C5D1 at predose (within 30 minutes prior to SOI) and at EOI (just before EOI).
25. Collect 1 PK sample at each subject's final visit.
26. Informed consent for optional genetics research should be obtained before collecting a sample.
27. Study drug administration ± 3 day window only.
28. Prophylaxis with prednisolone phosphate 1% or dexamethasone 0.1% 1 drop QID x 4 days starting 1 day prior to treatment
29. All participants should be followed for survival for 1 year from last subject last dose. and whether subsequent treatment for disease was given. Subject does not need to come in for visit. Participants who have completed treatment or the 3 month follow up visit (end of study) prior to amendment 5 will be reconsented for further follow up and survival status.
30. e-Diary to be completed at screening, then Days 1-7, 8, 15 of each treatment cycle. Upon implementation of the e-Diary, these assessments will be required.
31. OSDI and NEI-VFQ-25 to be administered during end of study treatment visit. Additional assessments for subjects who are experiencing corneal symptoms to be completed via telephone on a monthly basis for up to 1 year, or until resolution of symptoms (whichever comes first) during the follow-up period.
32. Exit interview to be performed within 21 days of end of study visit

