16.3. Appendix 3: Assessment Windows

No assessment windows will be applied.

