CUMAMTCT	Cumulative dose to TTECORTOX (mg)		For corneal toxicity that occurred on dosing days, the dose on the corneal toxicity day was not included in the cumulative dose calculation.	adex. adae
Q4CUMAMTCT	Quartile of CUMAMTCT	0,1,2,3		derived
Q5CUMAMTCT	Quintile of CUMAMTCT	0,1,2,3,4		derived
CUMAUCCT	Cumulative AUC to TTECORTOX (ug.day/mL)		(Cumulative dose to TTECORTOX)/Individual Clearance of ADC	popPK output, adae
Q4CUMAUCCT	Quartile of CUMAUCCT	0,1,2,3		derived
Q5CUMAUCCT	Quintile of CUMAUCCT	0,1,2,3,4		derived
TAAUCCT	Time-average AUC till TTECORTOX (AUC/day)		The area under the plasma ADC concentration–time curve (AUC) per day (AUC/day) will be derived for each patient using the available ADC dosing information, individual patient oral clearance (CL/F) values from the population pharmacokinetic model, and the time to the occurrence of the corneal toxicity.	popPK output, adae
Q4TAAUCCT	Quartile of TAAUCCT	0,1,2,3		derived
Q5TAAUCCT	Quintile of TAAUCCT	0,1,2,3,4		derived
CANCER	Cancer type	0 or 1	0=Multiple Myeloma, 1=BCMA positive Lymphomas If TRT01AN = 12, then CANCER=1, else	adsl

Column Header	Data Item	Codes	Derivation/Comments	Source data set
			CANCER=0	
AMT	Amount (in mg) of GSK2857916 given in first cycle		AMT = AVAL when PARAMCD=ALTDOS and AVISIT=CYCLE 1 DAY 1	adex
Q4AMT	Quartile of AMT	0,1,2,3		derived
Q5AMT	Quintile of AMT	0,1,2,3,4		derived
TOTAMT	Total dose received (mg)		TOTAMT = AVAL * WEIGHTBL; Get AVAL for PARAMCD=CUMDOSE	adex,adsl
Q4TOTAMT	Quartile of TOTAMT	0,1,2,3		derived
Q5TOTAMT	Quintile of TOTAMT	0,1,2,3,4		derived
IDOSE	GSK2857916 initial cycle dose (mg/kg)	>0	IDOSE=adex.TRT01A; strip off units	adex
Q4IDOSE	Quartile of IDOSE	0,1,2,3		derived
Q5IDOSE	Quintile of IDOSE	0,1,2,3,4		derived
CMAx	First dose Cmax of ADC – Observed EOI on Cycle 1 (ng/mL)			popPK output
Q4CMAx	Quartile of CMAx	0,1,2,3		derived
Q5CMAx	Quintile of CMAx	0,1,2,3,4		derived
MMAFCMAx	First dose Cmax of MMAF – Observed EOI on Cycle 1 (ng/mL)			popPK output
Q4MMAFCMAx	Quartile of MMAFCMAx	0,1,2,3		derived
Q5MMAFCMAx	Quintile of MMAFCMAx	0,1,2,3,4		derived
CTAU	First dose C _{tau} of ADC– Observed pre-dose on Cycle 2			popPK output
Q4CTAU	Quartile of CTAU	0,1,2,3		derived
Q5CTAU	Quintile of CTAU	0,1,2,3,4		derived
AUC	First dose AUC(0-inf) of ADC (ug.day/mL)		First dose (mg)/Individual Clearance of ADC	popPK output
Q4AUC	Quartile of AUC	0,1,2,3		derived
Q5AUC	Quintile of AUC	0,1,2,3,4		derived

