16.10.2.2. Exposure-Response Analyses**16.10.2.2.1. Corneal Toxicity**

Presence or absence of corneal toxicity will be described using a conventional logistic regression model for both \geq Grade 1 and \geq Grade 2 toxicity. Time to first corneal toxicity will be explored using Kaplan Meier plots with exposure subdivided into quartiles and quintiles. Severity of corneal toxicity will be analyzed using an ordered logistic regression model assuming Grades 0 (no toxicity), 1, 2 and 3, with exposure subdivided into quartiles and quintiles.

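### First-dose CTAU in the exposure-response datasets is the observed Cycle 2 pre-dose value with no time, delay or missing-data rule, so it falls when Cycle 2 is late and is absent when Cycle 2 is never given

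*SAP*

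**What the plan says.** SAP Section 16.10.1 specifies two datasets, one for corneal toxicity and one for efficacy. Each contains CTAU, described as the first-dose Ctau of the ADC and identified as "Observed pre-dose on Cycle 2". The derivation cell is empty and the source column names the population PK output. CTAU is then categorised ("Quartile of CTAU", and likewise quintiles). Sections 16.10.2.2.1 and 16.10.2.2.2 use exposure in that form: time to first corneal toxicity, for example, is explored by Kaplan-Meier "with exposure subdivided into quartiles and quintiles".

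The sample follows the infusion, not the calendar. In the Part 2 myeloma schedule (Section 16.2.3.1, footnote 24) PK samples are due on "C2D1, C3D1, and C5D1 at predose (within 30 minutes prior to SOI", where SOI is the start of infusion. Appendix 3 (Section 16.3) states "No assessment windows will be applied".

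Delays are expected. Section 6.5 measures them against the previous dose plus 21 days and says "The number and percentage of the delays 1-21, 22-42 and >42 days will be computed". The accumulation-ratio analysis in Section 9.3.1 does deal with them. One of its steady-state criteria is "Subjects who receive the same dose without delay or change for Cycles 1, 2, and 3", which tolerates at most 3 days, and of its model it says "The model will be adjusted by actual dose and dose delay status in each cycle". CTAU has no comparable provision.

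**The concern.** A first-dose trough is meant to describe exposure at a fixed time, here 21 days after the first dose. As specified, the time floats. A subject whose second dose comes three weeks late contributes a day-42 concentration that is handled as if it were a day-21 one.

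This matters most in the corneal analysis, because the outcome can influence the predictor. A corneal event that begins before the second dose and postpones it lowers that subject's CTAU. Such subjects drift into the bottom exposure category, which can mask a true positive relation or make it look inverse. The SAP treats this path as possible: corneal onset in days 1-21 is a reporting band (Section 8.2), and corneal events leading to dose interruptions or delays have their own tables (3.0160 to 3.0163).

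Missingness is a separate problem. A subject who stops after one dose has no Cycle 2 pre-dose sample. The imputation rule in Section 16.9.2 covers PopPK covariates, not CTAU. Every CTAU analysis is therefore conditioned on reaching Cycle 2.

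**Working it through.** The plan gives no figure to reproduce, because the point concerns a definition. The check has three parts.

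**1. How far a delay moves CTAU.** Assume mono-exponential decline after day 21:

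ratio to the day-21 value = 2^(-delay / half-life)

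The SAP gives no ADC half-life, so a range is assumed.

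| Assumed half-life | 7-day delay | 21-day delay |
|---|---|---|
| 5 days | 2^(-7/5) = 0.38 | 2^(-21/5) = 0.05 |
| 8 days | 2^(-7/8) = 0.55 | 2^(-21/8) = 0.16 |
| 12 days | 2^(-7/12) = 0.67 | 2^(-21/12) = 0.30 |
| 15 days | 2^(-7/15) = 0.72 | 2^(-21/15) = 0.38 |

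**2. What that does when no true relation exists.** Simulation with 38 subjects, half with an event, log-SD of the true trough 0.6, event independent of the trough and a 12-day half-life. A share of event subjects is delayed and the event is modelled by logistic regression on CTAU. All inputs are assumptions.

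| Event subjects delayed | Delay | Apparent OR per SD of CTAU | p < 0.05 |
|---|---|---|---|
| 40% | 21 days | 0.49 | 44% |
| 20% | 21 days | 0.68 | 14% |
| 10% | 21 days | 0.84 | 6% |
| 20% | 7 days | 0.87 | 5% |

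A second simulation used 35 subjects, a 30% event rate, log-SD 0.6 and a t-test on log CTAU. With a quarter of event subjects delayed 7 days, the rejection rate was 13%, 7% and 6% for half-lives of 7, 14 and 21 days. With half of them delayed 21 days it was 84%, 52% and 27%. The direction is always the same, lower apparent exposure in subjects with toxicity. The size depends on how many early events delay Cycle 2, by how long, and on the half-life.

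**3. What the delay does not touch.** First-dose AUC in Section 16.10.1 is dose divided by individual clearance, and CMAX is the Cycle 1 end-of-infusion value. Neither depends on when Cycle 2 is given. A trough evaluated at a nominal 21 days has a delay factor of 1.00 for any delay.

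**The case against.** The best defence is that the row is ambiguous rather than wrong. Its source is the population PK output, Section 16.9.2 plans individual Cycle 1 exposure measures, and Section 16.10.1 requires deviations from the dataset specification to be documented. A pre-next-dose sample is also how the SAP defines a trough elsewhere (Sections 9.1.2.1 and 9.3.1.3). This does not settle the matter. The item says observed, and following it literally would not be a deviation. The usual trough definition is fine for description but weak as a predictor of an event that can postpone the next dose.

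Several limits do stand:

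- A reader might infer that the causal direction is reversed throughout. The documents do not support that. Only a corneal event that starts before the second dose and delays it has this effect. The delay bands in Section 6.5 are reporting categories over all cycles and do not show that Cycle 2 is often late.
- Corneal toxicity is the only toxicity in the exposure-response plan. Hematologic or other unrelated delays mainly add error.
- The 44% figure is not an expected error rate. It needs one subject in five (40% of 50%) to have a very early event with a three-week delay. It also assumes a single dose level: adding an assumed 30 Part 1 subjects across all doses gives 22%, and restricting to 0.96 mg/kg and above gives 62%. The plan sets no significance threshold for these analyses.
- The 3-day tolerance in Section 9.3.1 identifies steady state. Its absence for CTAU is an unaddressed gap, not a contradiction.
- Early failures are lost from the CTAU analyses only, not from the whole exposure-response evaluation.

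**Conclusion.** The definition should be corrected in both datasets. Followed as written, CTAU is not a concentration at a fixed time. With half-lives of 5 to 15 days assumed, it falls to 38-72% of its day-21 value after a 7-day delay and 5-38% after a 21-day delay. Where early corneal events cause the delay, the CTAU-corneal relation is biased towards null or inverse. Short or rare delays have little effect at a 12-day half-life (about 5-6% of null simulations reach p < 0.05) and somewhat more at shorter half-lives. Large inflation needs frequent, long, event-driven delays, for which the SAP offers no evidence. Conditioning on Cycle 2 does not depend on these assumptions: without a second dose there is no value and no rule for its absence.

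The consequence is contained. CTAU is one of several exposure metrics, first-dose CMAX and AUC would visibly disagree with a spurious CTAU pattern, and the work is exploratory and reported separately.

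**What to change.** In both datasets, define CTAU as the individual PopPK-predicted ADC concentration at a nominal 21 days after the first dose, computed from the first dose only, for all subjects with PopPK estimates. This agrees with the source column and the Cycle 1 measures already planned. Keep the observed Cycle 2 pre-dose value as a check in subjects whose Cycle 2 dose was delayed by no more than 3 days.

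The cost is one derivation line in each specification and no new data. There is one drawback. In the Part 2 myeloma schedule, the only PK samples before Cycle 2 are pre-dose and end of infusion on Cycle 1 Day 1, with one more at the final visit (Section 16.2.3.1, footnotes 24 and 25). For subjects without a Cycle 2 sample the prediction therefore rests largely on the population model. Flag these subjects and repeat the CTAU analysis without them as a sensitivity check.

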7.3.1.2.3. Duration of Response

Duration of Response (DOR) is defined, for subjects with a confirmed response (PR or better) as the time between first documented evidence of confirmed response and disease progression or death due to PD, whichever occurs first.

- Duration of response is derived for patients with a confirmed PR or better only.
- Censoring rules will follow those of the TTP analysis.

DOR will be summarized using Kaplan-Meier curves. If there are a sufficient number of progressions or death due to PD among the responders, median DOR, first and third quartiles and 95% CI, will be estimated using the Brookmeyer-Crowley method [Brookmeyer, 1982]. A figure and listing of DOR time will also be provided. Summary and figure of DOR will be based on Part 2 MM population and subgroup: prior anti-cancer therapy of interest; listing of DOR will be based on All Treated MM population.

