16.9. Appendix 9: Population Pharmacokinetic (PopPK) Analyses

16.9.1. Population Pharmacokinetic (PopPK) Dataset Specification

Any deviations between the dataset specification and the final dataset will be documented in the population pharmacokinetic analysis report.

General Description:

1. The type of variables should be either NUM or DATE/TIME unless specified otherwise
2. The dataset is sorted by ID, RTFDD, ANALN, ASCENDING EVID unless specified otherwise
3. The data items (columns) in the analysis-ready data file will be in the same order as follows.
4. Exclude observations with DTYPE=IMPUTE
5. Include PKFL=Y (applicable to all datasets)
6. Same rules are applied for other baseline covariates. Baseline rules are as follows:
 - Use baseline value as defined by Stats in the lab test datasets;
 - If not defined by Stats, set to measurement nearest to, but prior to, time of first dose
 - Only in cases where Day 1 measurement is not available, but screening measurement is, the screening values will be used.
7. 3 significant figures for all values.

Column Header	Data Item	Codes	Derivation/Comments	Source data set
C	Line number/exclusion identifier	Row Number STM DRM PFD	Set to line/row number unless one or more of the following conditions are met, then set to code: 
 • STM = If a PK sample was taken but the date and/or time of the sample is missing and cannot be derived • DRM= PK samples for which dosing records are missing • PFD=PK samples with CONC reported as NA/NR/NQ/BQL/missing at pre-dose in CYCLE =1 	derived
STUDY	Study ID		1 = BMA117159	adpc
SUBJID	Subject identifier from source data		SUBJID = SUBJID	adsl
ID	NONMEM subject identifier		Sequential subject identifier across studies after data is sorted by SUBJID. Starting with P	derived

Column Header	Data Item	Codes	Derivation/Comments	Source data set
AMT	Amount of GSK2857916 given (in mg)		AMT = ALTDOSE, where PARAMCD=ALTDOSE only on the dosing line. For all other lines use "."	adex
INFD	Infusion Duration (day)		(AENDTM-ASTDTM)/60/60/24 This value will only be used on the dosing line. For all other lines use "."	adex
INFH	Infusion Duration (h)		(AENDTM-ASTDTM)/60/60 This value will only be used on the dosing line. For all other lines use "."	adex

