TOTAUC	Total AUC (ug.day/mL)		(Total dose received)/Individual Clearance of ADC	popPK output
Q4TOTAUC	Quartile of TOTAUC	0,1,2,3		derived
Q5TOTAUC	Quintile of TOTAUC	0,1,2,3,4		derived
MMAFAUC	First dose AUC(0-inf) of MMAF (ug.day/mL)		First dose (mg)/Individual Clearance of MMAF	popPK output
Q4MMAFAUC	Quartile of MMAFAUC	0,1,2,3		derived
Q5MMAFAUC	Quintile of MMAFAUC	0,1,2,3,4		derived
MMAFTOTAUC	Total AUC (ug.day/mL)		(Total dose received)/Individual Clearance of MMAF	popPK output
Q4MMAFTOTAUC	Quartile of MMAFTOTAUC	0,1,2,3		derived
Q5MMAFTOTAUC	Quintile of MMAFTOTAUC	0,1,2,3,4		derived

For efficacy

Column Header	Data Item	Codes	Derivation/Comments	Source data set
C	Exclusion identifier	Row Number DORDM	Set to line/row number unless one or more of the following conditions are met, then set to code: 
 DORDM: If DORD is missing 	adtte
STUDY	Study ID		1 = BMA117159	adsl
SUBJID	Subject identifier from source data		SUBJID = SUBJID	adsl
ID	NONMEM subject identifier		Sequential subject identifier across studies after data is sorted by SUBJID. Starting with P	derived
PFSCFLCD	PFS Censoring Flag Code	0 or 1	For PARAMCD=PFS_D, CNSR value is assigned to PFSCFLCD 0=Event 1=Censor	adtte
PFSD	PFS (Days)		For PARAMCD=PFS_D, AVAL value is assigned to PFSD	adtte
PFSM	PFS (Months)		For PARAMCD=PFS_M, AVAL value is assigned to PFSM	adtte
PFSY	PFS (Years)		For PARAMCD=PFS_D, (AVAL/365) value is assigned to PFSY	derived
TTRCFLCD	TTR Censoring Flag Code	0 or 1	For PARAMCD=TTR_D, Assign 1 to TTRCFLCD. For subjects where TTR_D is missing, assign 0 to TTRCFLCD.	adtte
TTRD	TTR (Days)		For PARAMCD=TTR_D, AVAL value is assigned to TTRD. For subjects where TTR_D is missing, assign PFSD to TTRD.	adtte
TTRM	TTR (Months)		For PARAMCD=TTR_M, AVAL value is assigned to TTRM. For subjects where TTR_M is missing, assign PFSM to TTRM.	adtte
TTRY	TTR (Years)		For PARAMCD=TTR_D, (AVAL/365) value is assigned to TTRY. For subjects where TTR_D is missing, assign PFSY to TTRY.	derived
DORCFLCD	DOR Censoring Flag Code	0 or 1	For PARAMCD=DOR_D, CNSR value is assigned to DORCFLCD 0=Event 1=Censor Assign "." for missing.	adtte
DORD	DOR (Days)		For PARAMCD=DOR_D, AVAL value is assigned to DORD. For subjects where DOR_D is missing, assign "."	adtte

Column Header	Data Item	Codes	Derivation/Comments	Source data set
DORM	DOR (Months)		For PARAMCD=DOR_M, AVAL value is assigned to DORM. For subjects where DOR_M is missing, assign “.”	adtte

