16.10.2.2.2. Clinical Response

Presence or absence of clinical response will be described using a conventional logistic regression model. Time to response will be explored using Kaplan Meier plots with exposure subdivided into quartiles and quintiles.

PFS will be explored using Kaplan Meier plots with exposure subdivided into quartiles and quintiles and occurrence of progression may also be described using a conventional logistic regression model.

Duration of response will be explored using Kaplan Meier plots with exposure subdivided into quartiles and quintiles.

Best clinical response will be analyzed using an ordered logistic regression, with response categorized from 0 (progressive disease) to 6 (stringent complete response). Exposure will be treated as a categorical variable subdivided into quartiles and quintiles.

In the ordered logistic regression analyses, the use of categorical measures of exposure in lieu of continuous variables will allow for non-parametric descriptions of response functions.

Best clinical response as assessed by maximum reduction in M-protein or FLC will be analyzed by exposure (continuous and/or by quartile and quintile of exposure).

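### The efficacy exposure-response dataset puts an exclusion code on every myeloma non-responder and does not limit that code to the duration-of-response analysis

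*SAP*

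**What the plan says.** SAP 16.10.1 specifies one dataset for the efficacy exposure-response analyses. Its first column, C, is labelled as an exclusion identifier and is filled as follows: "Set to line/row number unless one or more of the following conditions are met, then set to code". One condition is listed: "DORDM: If DORD is missing".

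SAP 7.3.1.2.3 fixes who has a DOR value: "Duration of response is derived for patients with a confirmed PR or better only". The DORD row of the dataset agrees with this. Its instruction "For subjects where DOR_D is missing, assign" is completed with a dot, meaning missing, and the DOR censoring flag (DORCFLCD) is treated in the same way.

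Other rows of the same dataset give non-responders values that can be analysed. For time to response (TTR), the time is filled in ("For subjects where TTR_D is missing, assign PFSD to TTRD") and so is the flag ("For subjects where TTR_D is missing, assign 0 to TTRCFLCD"). ORDRESP codes PD, SD and MR as 0, 1 and 2. The PFS rows carry no responder condition.

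SAP 16.10.2.2.2 then plans the models. The first is "Presence or absence of clinical response will be described using a conventional logistic regression model". It is followed by Kaplan-Meier plots of TTR, PFS and DOR by exposure group, an ordered logistic model of best response on levels 0 to 6, and an analysis of maximum reduction in M-protein or FLC. None of these except DOR is confined to responders.

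**The concern.** An exclusion code should mark records that cannot be used. Here its trigger is an outcome: a subject receives the code for not having responded, not because of a data defect. A programmer or modeller who filters on column C before fitting would select the analysis set on the endpoint under study.

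The plan's other datasets make that use plausible. In the population PK dataset (SAP 16.9.1), column C is the "Line number/exclusion identifier" and its codes mark a missing sample time, a missing dosing record or an unusable pre-dose value. SAP 16.9.2 separately allows concentrations with missing dosing or sampling times to be excluded. The corneal toxicity dataset in SAP 16.10.1 sets column C to the row number only, adds a line for each subject without an event, and codes that subject 0. The efficacy dataset departs from this pattern.

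At stake is the exploratory objective in SAP 2.2 of relating exposure to clinical activity. That relation cannot be estimated if only responders remain.

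**Working it through.** The plan gives no figure to reproduce. The check traces the derivation and then sets the code beside the planned analyses.

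**Who receives the code**

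1. DOR is derived only for confirmed PR or better (SAP 7.3.1.2.3).
2. DORD is therefore missing for every myeloma subject whose best confirmed response is MR, SD, PD or NE (SAP 16.10.1, DORD row).
3. Missing DORD sets column C to DORDM (SAP 16.10.1, column C).
4. So every myeloma non-responder is coded. DOR is defined for myeloma only, so any lymphoma subject in the dataset would also be coded whatever the response, but the stated analysis is in myeloma.

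**How many, for illustration**

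Inputs: N = 40, the maximum Part 2 myeloma sample size, and true ORR of 20% and 40%, all from SAP 3.1.2.1.1. These are design assumptions, not results.

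Coded subjects = N × (1 − ORR)

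- ORR 40%: 40 × (1 − 0.40) = 24 coded (24/40 = 60%); 40 − 24 = 16 not coded.
- ORR 20%: 40 × (1 − 0.20) = 32 coded (32/40 = 80%); 40 − 32 = 8 not coded.

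These are counts of rows that carry the code.

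**What follows if coded rows are dropped from the whole dataset**

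| Planned analysis (SAP 16.10.2.2.2) | Needs | Left after exclusion |
|---|---|---|
| Logistic model of response | Responders and non-responders | Constant outcome; cannot be fitted |
| Ordered model of best response | ORDRESP 0 to 6 | Levels 3 to 6 only |
| TTR by exposure group | Non-responders with flag 0 and PFS time | No censored subjects |
| PFS by exposure group | All subjects | PFS conditioned on response |
| M-protein/FLC reduction by exposure | All subjects with a value | Responders only |
| DOR by exposure group | Responders only | Unchanged |

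Only the DOR row survives intact. DORD and DORCFLCD are already missing for non-responders, so those subjects cannot enter the DOR curves even without the code. DORDM is thus redundant for the one analysis it is named after, and could change a result only in the others.

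**The case against.** The strongest reply is that a reader might infer from column C that the response, PFS and best-response models would be run on responders only, and that the SAP does not say so. This is correct. No section orders coded rows to be dropped from those models, and SAP 16.10.2.2 has no exclusion rule. The population PK comparison is imperfect, because there the methods section separately describes exclusions, and no such text exists for DORDM. The TTR fill-in rules and ORDRESP levels 0 to 2 would be pointless if non-responders were removed, so the evident intent is to keep them. The code is also named after one endpoint, and a DOR-only reading makes the specification coherent.

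A global exclusion would also show itself at once in the logistic model, whose outcome would be constant. The analysis is exploratory and reported separately, and the plan allows documented deviations from the dataset specification. The main ORR estimate and the main PFS and DOR summaries do not use this dataset.

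All of this stands, and it limits both the claim and its severity. It does not remove the defect: the intent has to be deduced against the column's own label. The logistic failure would be visible, but the PFS and TTR curves, the ordered model on levels 3 to 6 and the M-protein/FLC analysis could all run without an error. The deviation clause records a departure afterwards; it does not say which rows belong in which model.

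**Conclusion.** The specification is wrong as written. It attaches an exclusion code to every myeloma non-responder, sets no endpoint limit on it, and so conflicts with other rows of the same table and with the planned models.

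The consequence is conditional. If the code is applied as an exclusion to the whole dataset, all non-responders are lost: 24 to 32 of 40 Part 2 subjects under the design's ORR assumptions of 40% to 20%. If it is applied to DOR only, nothing is lost. The SAP does not say which, so it cannot be concluded that responder-only models are planned.

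It would also go too far to say that the lost Part 1 low-dose non-responders supply most of the exposure contrast. The SAP lists the Part 1 dose levels but gives no subject numbers or responses by dose.

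Severity is minor to moderate: a real contradiction in an exploratory, separately reported analysis.

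**What to change.** Either of two edits to column C of the efficacy dataset in SAP 16.10.1 resolves it:

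- set column C to the row number for all subjects and delete DORDM; or
- keep DORDM and state that it applies to the DOR Kaplan-Meier analysis only.

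No new responder flag is needed, since missing DORD and DORCFLCD already identify the subjects without a DOR.

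With either edit, add a sentence to SAP 16.10.2.2.2 stating that the response, TTR, PFS, best-response and maximum-reduction (MAXPRED) analyses keep all treated myeloma subjects with exposure data.

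The cost is one row of the specification and one sentence of methods. No new data are needed.
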